11.4.3 Statistical Analysis of PK Data

Dose Proportionality

Dose proportionality will be assessed by performing a regression analysis of the log-transformed C_{\max} , AUC_{0-t} , AUC_{0-24} and $AUC_{0-\infty}$ values versus the log-transformed dose using the power model with a fixed

effect for log(dose). For each parameter, point estimates for the intercept and the slope of the regression line and the 95% CI of the slope will be calculated. In addition, estimated geometric LSMeans and corresponding 95% CIs will be presented for each dose level.

The power model is defined as:

$$\log_e(C_{\max}, AUC_{0-t}, AUC_{0-inf}) = \alpha + \beta \log_e(\text{Dose}) + \varepsilon,$$

where α is the intercept, β is the slope and ε is the error term.

Geometric LSMeans and associated 95% CIs along with individual subject values for the derived pharmacokinetic parameters C_{\max} , AUC_{0-t} and AUC_{0-inf} will be presented graphically versus dose with each parameter presented on a separate plot.

Dose Independence

Dose independence will be assessed for $t_{1/2}$ and CL/F by performing a regression analysis of the untransformed parameters versus dose with a fixed effect for dose. For each parameter, point estimates for the intercept and the slope of the regression line and the 95% CI of the slope will be calculated. In addition, estimated LSMeans and corresponding 95% CIs will be presented for each dose level.

LSmeans and associated 95% CIs along with individual subject values for the derived pharmacokinetic parameters $t_{1/2}$ and CL/F will be presented graphically versus dose.

11.4.3.1 Part B – Food Effect

Following logarithmic transformation, C_{\max} , AUC_{0-t} and AUC_{0-inf} values will be subjected to an analysis of variance (ANOVA) including fixed effects for sequence, period, treatment and subject nested within sequence. Point estimates and 90% confidence intervals will be constructed for the contrasts between treatments using the residual mean square error obtained from the ANOVA. The point and interval estimates will be back-transformed to give estimates of the ratios of the geometric LSMeans and corresponding 90% CIs. In addition, estimated geometric LSMeans and corresponding 95% CIs for each treatment and the within-subject CV% will be presented.

The geometric LSMean ratios and corresponding 90% CIs for C_{\max} AUC_{0-t} and AUC_{0-inf} will be represented graphically (a plot with error bars) with all parameters on one graph. On the same graph, points indicating individual within-subject ratios for the three PK parameters will be presented. Reference lines will be included to indicate the 80.00% and 125.00% CI thresholds.

Each treatment comparison will be analysed separately and will only include data from subjects who are included in the PK Set for the two treatments being evaluated.

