Derived PK parameters will be listed along with the points used to calculate k_{el} (lower, upper, and number used) and coefficient of determination (R^2) adjusted. The derived PK parameters will also be summarised. The descriptive statistics presented will be N, n, arithmetic mean, geometric mean (with the exception of T_{\max}), SD, coefficient of variation (CV%), minimum, median, and maximum.

Part A (SAD): Dose Proportionality/Independence. Dose proportionality will be assessed by performing a regression analysis of the log-transformed C_{\max} , AUC_{0-t} and $AUC_{0-\infty}$ values versus the log-transformed dose using the power model with a fixed effect for log (dose). For each parameter, a point estimate and 95 % confidence interval (CI) will be calculated for the slope of the regression line.

Dose independence will be assessed for $t_{1/2}$ and CL/F by performing a regression analysis of the untransformed parameters versus dose with a fixed effect for dose. For each parameter, a

point estimate and corresponding 95 % CI will be calculated for the slope of the regression line.

Part B (Food Effect): Following logarithmic transformation, C_{max} , AUC_{0-t} and AUC_{0-inf} values will be subjected to an ANOVA including fixed effects for treatment and participant. Point estimates and 90% CI will be constructed for the contrasts between treatments using the residual mean square error obtained from the ANOVA. The point and interval estimates will be back-transformed to give estimates of the ratios of the geometric least squares means (LSmeans) and corresponding 90% CI. Estimated geometric means will also be presented for each treatment.

Part C (MAD)

Dose Proportionality/Independence: For Day 1 and Final Dosing Day (Day 10), dose proportionality will be assessed by performing a regression analysis of the log-transformed C_{max} , AUC_{0-t} and AUC_{0-inf} (Day 1 only) values versus the log-transformed dose using the power model with a fixed effect for log (dose). For each parameter, a point estimate and 95 % CI will be calculated for the slope of the regression line.

For Final Dosing Day (Day 10), dose independence will be assessed for $t_{1/2}$ and CL/F by performing a regression analysis of the untransformed parameters versus dose with a fixed effect for dose. For each parameter, a point estimate and corresponding 95 % CI will be calculated for the slope of the regression line.

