3.1 OVERVIEW

This is a phase I, randomised, double-blind, placebo-controlled study to investigate the safety, tolerability, and PK of AX-158 in healthy male participants following single (Part A) and multiple (Part C) ascending doses including food effect (Part B).

The study will be conducted in three parts:

Part A

Part A (SAD) will enrol up to 8 participants per cohort randomised (3:1) to receive AX-158 or placebo. Part A will follow a single ascending dose (SAD) design with all participants receiving one dose of AX-158 (or placebo) in the fasted state.

This part will be conducted in up to 34 participants (8 participants in cohorts 1 and 5, 6 participants in cohorts 2, 3 and 4). An additional two cohorts of up to eight (8) participants each (up to 16 additional participants total) may be investigated if required.

Part B

Part B (Food Effect) will be conducted in up to 8 participants in a cross-over manner; each participant will receive AX-158 in the fed and fasted state.

This part will be conducted in up to 8 participants in a cross-over manner.

Part C

Part C (MAD) will enrol up to 8 participants per cohort randomised to (3:1) to receive AX-158 or placebo. Part C will follow a multiple ascending dose (MAD) design with participants receiving AX-158 (or placebo) once daily for 10 consecutive days, in a fed or fasted state (depending on the outcome of the Part B (Food Effect)). Doses, dosing duration and dose regimen (i.e., q.i.d., b.i.d., t.i.d.) of AX-158 and matching placebo for Part C may be modified based on all available safety, tolerability, and PK data and applied to additional MAD cohorts.

This part will be conducted in up to twenty-four (24) participants (3 cohorts of up to 8 participants). An additional two cohorts of up to eight (8) participants each (up to 16 additional participants total) may be investigated if required.

Duration of study:

- Part A: approximately 6 weeks for each individual (from the screening to post-study follow-up).
- Part B: approximately 8 weeks for each individual (from the screening to post-study follow-up).
- Part C: approximately 7 weeks for each individual (from the screening to post-study follow-up).

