11.4.3.4 Part C (MAD) - Accumulation

For each dose level, log-transformed C_{\max} and $AUC_{0-\tau}$ (only applicable if non-q.d. dosing regimen is implemented) values on Day 1 and Final Dosing Day (Day 10) will be subjected to an ANOVA with study day as a fixed effect and subject as a random effect. For comparison, point estimates and 90% CIs for the difference between Day 10 and Day 1 will be constructed using the residual mean square error obtained from the ANOVA for each dose level. The point and interval estimates will then be back transformed to give estimates of the ratios of the geometric LSMeans and corresponding 90% CIs. In addition, estimated geometric LSMeans and corresponding 95% CIs will be presented for each study day.

The geometric LSMean ratios and corresponding 90% CIs for C_{\max} and $AUC_{0-\tau}$ will be represented graphically (a plot with error bars) with all dose levels on one graph, one graph per parameter. On the same graph, points indicating individual within-subject ratios will be presented.

Statistical analysis of PK parameters will be performed using the PK set.

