Results for C_{max} , AUC_{0-t} and AUC_{0-inf} obtained using a regression analysis on log-transformed values versus log-transformed dose using the power model. Results for CL/F and $t_{1/2}$ obtained using a fixed effects ANOVA on non-transformed data with a fixed effect of dose.*Programming Note: A similar figure will be presented for Part C (MAD), including C_{max} and AUC_{0-tau} results for Day 1 and Day 10 and AUC_{0-inf} , $t_{1/2}$ and CL/F for Day 10, with treatment footnote as presented in Table 14.3.1.1.*

AX-158-101
Table 14.4.2.4
Summary of Statistical Analysis of Plasma AX-158 Food Effect - Part B
PK Set

Parameter	Geometric LSMeans (95% CI)		Geometric LSMean Ratio (%) (90% CI) [Within-Subject CV%]
	15 mg AX-158 - Fed (N=x)	15 mg AX-158 - Fasted (N=x)	Fed / Fasted
C _{max} (<units>)	xx.x (xx.x - xx.x)	xx.x (xx.x - xx.x)	xx.x (xx.x - xx.x) [xx.x]
AUC _{0-t} (<units>)	xx.x (xx.x - xx.x)	xx.x (xx.x - xx.x)	xx.x (xx.x - xx.x) [xx.x]
AUC _{0-inf} (<units>)	xx.x (xx.x - xx.x)	xx.x (xx.x - xx.x)	xx.x (xx.x - xx.x) [xx.x]

Source Listing: 16.2.5.2 Produced: yyyy-mm-ddThh:mm - Page x of y
Treatment = a single dose of 15 mg AX-158 capsules over 2 treatment periods, in the fed and fasted state.
Results obtained using an ANOVA with fixed effects of treatment, period, sequence and subject
nested within sequence.

AX-158-101

Figure 14.4.2.2

Food Effect Least Squares Geometric Mean Ratios and 90% CI of Plasma AX-158 PK Data - Part B (Food Effect)
PK Set**Figure Specifications**

Plot type: Least squares geometric mean ratios (with 90% CI) overlaid with individual subject ratios.

By: Parameter - C_{max} , AUC_{0-t} and AUC_{0-inf} displayed on one plot.

x axis: Parameter

x axis: Label each parameter including units

x axis: values: 3 PK parameters (C_{max} , AUC_{0-t} , AUC_{0-inf})

Y axis: Least squares geometric mean ratio and 90% CI, with individual subject ratios

Y axis Label: Ratio (90% CI) (%)

Y axis values: As appropriate

Legend:

15 mg AX-158 - Fed / 15 mg AX-158 - Fasted

Source Listing: 16.2.5.2; Produced: yyyy-mm-ddThh:mm - Page x of y

Treatment == a single dose of 15 mg AX-158 capsules over 2 treatment periods, in the fed and fasted state.

Results obtained using an ANOVA with fixed effects for fed/faasted state and subject.

Version: 3.0
Document Title: SAP Template - Phase 1
Document Number: TEMP-00109
Previous Document Number: STATt008

AX-158-101
Table 14.4.2.5

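### The Part B 95% CIs for the fed and fasted geometric LSMeans carry within-subject error only, so as intervals for population geometric means they are too narrow, by an amount set by the ratio of between- to within-subject SD

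*SAP*

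**What the plan says.** SAP section 11.4.3.1 specifies a single Part B model for log Cmax, AUC0-t and AUC0-inf, "including fixed effects for sequence, period, treatment and subject nested within sequence". The food-effect inference comes from it: "Point estimates and 90% confidence intervals will be constructed for the contrasts between treatments using the residual mean square error obtained from the ANOVA". The same paragraph adds per-treatment output: "In addition, estimated geometric LSMeans and corresponding 95% CIs for each treatment and the within-subject CV% will be presented".

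The Table 14.4.2.4 shell (SAP section 15) gives the fed and fasted geometric LSMeans a 95% CI beside the ratio. Its footnote covers the whole table: "Results obtained using an ANOVA with fixed effects of treatment, period, sequence and subject" nested within sequence. No random term and no other standard error is named for the LSMean column. The Figure 14.4.2.2 footnote names a different model (food state and subject only), but subject is fixed there too.

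Protocol section 10.11.8 also has participant as a fixed effect, but asks for less: "Estimated geometric means will also be presented for each treatment", with no interval. The 95% CI is therefore a SAP addition. SAP section 1.2 records the change of model but not the added CI.

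For the same kind of output in Part C accumulation, the data "will be subjected to an ANOVA with study day as a fixed effect and subject as a random effect" (section 11.4.3.4).

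**The concern.** A fixed-subject ANOVA suits a within-subject contrast, because each man's own level cancels between fed and fasted. It does not suit the mean under one condition. There the subject's level does not cancel, and treating the 8 subject effects as fixed constants removes their sampling variability from the standard error. The result describes the average of these 8 men, while the table labels it as a 95% CI with no such restriction.

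What is at stake is how precisely the report appears to know absolute exposure in each food state. A reader taking the column at face value would think the fed and fasted geometric means better estimated than they are.

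**Working it through.** The plan gives no CI width, CV or power to reproduce; SAP section 3.5 says the sample size has no formal statistical basis. The check is therefore algebra, followed by numbers over assumed CVs.

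**Inputs from the documents**
- Subjects: "Part B (Food Effect) will be conducted in up to 8 participants in a cross-over manner" (SAP section 3.1).
- Paired data: the analysis "will only include data from subjects who are included in the PK Set for the two treatments being evaluated" (section 11.4.3.1).
- Subject(sequence) is fixed (section 11.4.3.1 and Table 14.4.2.4).

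**Assumptions**
- All 8 men complete, 4 per sequence.
- Between-subject CV 20-60% and within-subject CV 15-30%.
- Log-scale SD = sqrt(ln(1 + CV²)).

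Write σb and σw for the between- and within-subject SDs on the log scale.

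**1. Variance as planned.** The 16 observations support 8 subject levels (sequence is absorbed in these), 1 period and 1 treatment parameter, leaving 16 − 10 = 6 residual df. Inverting the design matrix gives Var(LSMean) = 0.125 × MSE = MSE/8. The 95% half-width is t(0.975, 6) × σw/√8, with t = 2.447. For the Fed − Fasted contrast the multiplier is 0.25, and no subject term enters.

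**2. Variance for a population mean.** With subject random, Var(LSMean) = (σb² + σw²)/8. It is estimated from the between-subject mean square, with expectation a = 2σb² + σw², and the residual mean square, with expectation b = σw², each on 6 df. The Satterthwaite df are 6(a + b)²/(a² + b²).

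**3. Shortfall.** The standard-error ratio is r = sqrt(1 + σb²/σw²). The width ratio is somewhat smaller than r, because the random-subject interval has more than 6 df. Coverage of the planned interval for the population mean is 1 − 2·P(T6 > 2.447/r).

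**4. Worked case, between-subject CV 40%, within-subject CV 20%.**
- σb = sqrt(ln 1.16) = 0.385; σw = sqrt(ln 1.04) = 0.198; total SD = sqrt(0.385² + 0.198²) = 0.433.
- r = 0.433/0.198 = 2.19.
- Planned half-width: 2.447 × 0.198/√8 = 0.171, so limits of ×/÷1.19.
- Random-subject: a = 0.336, b = 0.039, df = 7.4, t = 2.34; half-width 2.34 × 0.433/√8 = 0.358, so limits of ×/÷1.43.
- Width ratio: 0.358/0.171 = 2.09. These limits insert the true SDs. The median limits over simulated trials are ×/÷1.18 and ×/÷1.40, with about the same ratio.
- Coverage: 1 − 2·P(T6 > 2.447/2.19 = 1.12) = 69%.

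**5. Range** (between-subject CV / within-subject CV)

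| Assumed CVs | SE ratio | Width ratio | Actual coverage of the 95% CI |
|---|---|---|---|
| 20% / 30% | 1.21 | 1.09 | 91% |
| 20% / 20% | 1.41 | 1.30 | 87% |
| 30% / 20% | 1.79 | 1.68 | 78% |
| 40% / 20% | 2.19 | 2.09 | 69% |
| 60% / 20% | 2.97 | 2.90 | 56% |
| 60% / 15% | 3.85 | 3.79 | 45% |

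Below this grid the effect fades. At 10% / 20% (σb/σw = 0.5) the SE ratio is 1.12, but the larger t value on 6 df offsets it: the two widths are equal and coverage is 93%.

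**6. Check by simulation.** Full 8-subject crossovers at σb/σw = 2 gave 68% coverage for the LSMean CI (formula 68%) and 90% for the 90% CI of the ratio. Simulating the mean squares across the grid in step 5, the random-subject interval covered about 95% throughout.

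**The case against.** The case for leaving the plan alone is reasonable, and much of it stands.

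- Nothing depends on this column. The Part B objective is the food effect, judged on the Fed/Fasted ratio and its 90% CI, and only the ratio has 80% and 125% reference lines. No escalation, dose-selection or fed/fasted rule cites an LSMean CI. This stands, and it limits the importance of the point.
- Between-subject spread is reported elsewhere. Table 14.4.2.1 is repeated for Part B with geometric mean, SD, CV% and range by treatment, and Listing 16.2.5.2 gives individual values. This also stands, but it does not correct an interval printed as 95% in another table.
- The interval is valid for the mean of these 8 men, and a fixed participant effect is the protocol's own choice. True, but the table states no such restriction, and the protocol attached no CI to the means.

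Three stronger readings are tempting. A reader might infer that the intervals are far too narrow. That needs σb/σw, which the documents do not give; with equal CVs the width factor is 1.3. A reader might infer that the food-effect result is compromised. It is not, because subject effects cancel in the contrast. A reader might also infer that a comparison of Part B with Part C LSMean CIs is spoiled. No section plans one, the Part C doses are left open in the shells, and the parameters largely differ: Part C analyses troughs, Cmax and, for accumulation, AUC0-tau only if dosing is not once daily. Part C shows only that the SAP uses a random-subject model for the same type of output.

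**Conclusion.** The point holds as a correction to a descriptive column. As written, the per-treatment 95% CIs omit between-subject variance and under-cover the population geometric mean whenever that variance is above zero. The existence of the error follows from the model alone; its size rests on assumed CVs. Over the grid used here, the standard error is too small by about 1.2 to 3.9 times, the width by about 1.1 to 3.8 times, and coverage is about 91% down to 45%. All figures assume 8 completers, 4 per sequence, and log-normal exposure. The documents support calling the intervals too narrow by an amount that grows with σb/σw. They do not support an unqualified claim of a large error, or any doubt about the ratio, its 90% CI or the within-subject CV%.

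**What to change.** Keep the fixed-effects ANOVA for the Fed/Fasted ratio, its 90% CI and the within-subject CV%. For the fed and fasted geometric LSMeans, do one of the following, in order of preference:

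1. Take the 95% CIs from a model with subject(sequence) random (for example PROC MIXED with Kenward-Roger df).
2. Drop these CIs and present the geometric means alone, as the protocol asks.
3. At minimum, add a footnote that they reflect within-subject error only and describe the participants studied.

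Change the Table 14.4.2.4 footnote to match the choice. In the same edit, align the Figure 14.4.2.2 footnote with the section 11.4.3.1 model.

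Cost: about two sentences of SAP text, two footnotes and, for option 1, a few lines of SAS. The ratio and its 90% CI stay as they are, because their model is untouched. The downside of option 1 is that the LSMean CIs will generally be wider.

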11.4.3.2 Part C (MAD) - Dose-Proportionality/Independence

Dose-Proportionality

For Day 1 and Final Dosing Day (Day 10), dose proportionality will be assessed by performing a regression analysis of the log-transformed C_{\max} , AUC_{0-tau} and AUC_{0-inf} (Day 10 only) values versus the log-transformed dose using the power model with a fixed effect for log (dose). For each parameter, a point estimate and 95 % CI will be calculated for the slope of the regression line.

Version: 3.0
Document Title: SAP Template - Phase 1
Document Number: TEMP-00109
Previous Document Number: STATt008

The power model is defined as:

$$\log_e(C_{\max}, AUC_{0-t}, AUC_{0-\infty}) = \alpha + \beta \log_e(\text{Dose}) + \varepsilon,$$

where α is the intercept, β is the slope and ε is the error term.

Geometric LSMeans and associated 95% CIs along with individual subject values for the derived pharmacokinetic parameters C_{\max} , AUC_{0-t} and $AUC_{0-\infty}$ will be presented graphically versus dose with each parameter presented on a separate plot.

Dose Independence

For Final Dosing Day (Day 10), dose independence will be assessed for $t^{1/2}$ and CL/F by performing a regression analysis of the untransformed parameters versus dose with a fixed effect for dose. For each parameter, a point estimate and corresponding 95 % CI will be calculated for the slope of the regression line.

11.4.3.3 Part C (MAD) - Steady State

For each treatment, log-transformed trough concentration levels at pre-dose on Day 5 and Final Dosing Day (Day 10) will be subjected to a mixed effects analysis of variance (ANOVA) with study day as a fixed effect and subject as a random effect in order to establish whether steady-state has been attained for each treatment. The point and interval estimates will be back-transformed to give estimates of the ratios of the geometric LSMeans and corresponding 90% CIs for the comparisons of each consecutive day (i.e. Day 10/Day 5). In addition, estimated geometric LSMeans and corresponding 95% CIs will be presented for each study day.

The geometric LSMean ratio and corresponding 90% CI for the Day 10/Day 5 comparison will be presented graphically (a plot with error bars) with all treatments on one graph. On the same graph, points indicating individual within-subject ratios for the comparison will be presented.

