- For all cohorts IMP or placebo will be administered orally in a fasted state (after an overnight fast of at least 10 h) with 240 mL water. The fast will be broken 4 h post-dose with lunch on Days 1-10.
- Urine sampling: for AX-158: pre-dose and in intervals of 0-12, 12-24, 24-48 and 48-72 h post-dose on Day 1 and Day 10
- Symptom Directed
- Pre-dose trough sample day 5 only
- COVID-19 test on day 8 and prior to check out.
- Additional samples will be taken based on emerging data

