11.4 PK ANALYSES

11.4.1 Concentration Data

Plasma PK samples will be collected for the measurement of AX-158 at the following time points:

Part A:

- Day 1 pre-dose, 30 mins, 45 mins, 1h, 2h, 3h, 4h, 6h, 8h, 12h
- Day 2: 24h, 36h
- Day 3: 48h
- Day 4: 72h

Part B: For both treatment periods

- Day 1 pre-dose, 30 mins, 45 mins, 1h, 2h, 3h, 4h, 6h, 8h, 12h
- Day 2: 24h, 36h
- Day 3: 48h
- Day 4: 72h

Part C:

- Day 1 and Day 10 pre-dose, 1h, 2h, 3h, 4h, 5h, 6h, 8h, 12h
- Day 2 and Day 11: 24h, 36h
- Day 3 and Day 12: 48h
- Day 4 and Day 13: 72h
- Day 5: pre-dose
- Day 6: Pre-dose
- Day 7: Pre-dose
- Day 8: Pre-dose

Plasma AX-158 concentrations will be listed along with blood sampling times and details of any sampling time deviations and summarised for each treatment using the descriptive statistics N, n, arithmetic mean,

geometric mean, arithmetic standard deviation (SD), coefficient of variation (CV%), minimum, median and maximum.

The individual subject plasma AX-158 concentration profiles over time will be presented graphically on both linear and semi-logarithmic scales with each subject on a separate plot. For Part C, Day 1 and Final Dosing Day (Day 10) profiles will be presented on the same plot. The geometric mean plasma AX-158 concentration profiles over time will be presented graphically on both linear and semi-logarithmic scales with all treatments on the same plot, with separate plots for Day 1 and Final Dosing Day profiles for Part C.

Urine PK samples will be collected for the measurement of AX-158 at the following time intervals: pre-dose and in intervals of 0-12, 12-24, 24-48 and 48-72 h post-dose on Day 1 and Day 10.

Urine AX-158 concentrations will be listed along with urine volumes and summarised for each treatment using the descriptive statistics N, n, arithmetic mean, geometric mean, arithmetic standard deviation (SD), coefficient of variation (CV%), minimum, median and maximum.

For inclusion within the summary tables and plots, plasma and urine concentrations below the lower limit of quantification (LLOQ) will be imputed as zero at pre-dose and as LLOQ/2 for post-dose samples. They will be listed as recorded. Data reported as not reportable or no sample/result will be handled as missing (i.e. no assumption will be made about the actual concentration).

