AUC_{0-24} ($\text{h}^*\mu\text{g/mL}$)	Area under the concentration-time curve (AUC) from the time of dosing to 24 h post-dose	AUC measured from the concentration at time of dosing to 24 hours post dose. The AUC is computed using the linear up-log down trapezoidal rule.	AUC0-24
$AUC_{0-\tau}$ ($\text{h}^*\mu\text{g/mL}$) (only required if non-q.d. dosing regimen)	Area under the plasma concentration-time curve (AUC) from the time of dosing to $<X>$ hours (dosing interval) after the Day $<X>$ dose.	AUC measured from the concentration at time of dosing to the concentration at $<X>$ hours. The AUC is computed using the linear up-log down trapezoidal rule.	AUC_TAU

Part C on Final Dosing Day:

Pharmacokinetic Parameter and Unit	Definition	Computation	WinNonlin Parameter Name
C_{max} ($\mu\text{g/mL}$)	Maximum concentration.	Maximum observed concentration, occurring at T_{max} . If not unique, then the first maximum is used.	Cmax
T_{max} (h)	The time to maximum observed concentration.	Time of maximum observed concentration. If the maximum observed concentration is not unique, then the first maximum is used.	Tmax

Pharmacokinetic Parameter and Unit	Definition	Computation	WinNonlin Parameter Name
λz (1/h)	Elimination rate constant.	First order rate constant associated with the terminal (log-linear) portion of the curve. Estimated by linear regression of time vs. log concentration; the regression analysis should contain data from at least 3 different time points in the terminal phase	lambda_z
$t_{1/2}$ (h)	Terminal elimination half-life.	$= \ln(2) / \lambda z$	HL_Lambda_z
AUC_{0-24} (h* μ g/mL)	Area under the concentration-time curve (AUC) from the time of dosing to 24 h post-dose	AUC measured from the concentration at time of dosing to 24 hours post dose. The AUC is computed using the linear up-log down trapezoidal rule.	AUC0-24
$AUC_{0-\tau}$ (h* μ g/mL) (only required if non-q.d. dosing regimen)	Area under the plasma concentration-time curve (AUC) from the time of dosing to 24 hours (dosing interval) after the Day 10 dose.	AUC measured from the concentration at time of dosing to the concentration at 24 hours. The AUC is computed using the linear up-log down trapezoidal rule.	AUC_TAU

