Summary of Statistical Analysis of Plasma AX-158 Steady State - Part C (MAD)
PK Set

Treatment	AX-158 Trough Concentration (<units>)		Geometric LSMean Ratio (90% CI)
	Geometric LSMeans (95% CI)	Day 10	
	Day 5	Day 10	Day 10/Day 5
Cohort <X>: AX-158<X> mg (N=x)	xxx (xx.xx, xx.xx)	xxx (xx.xx - xx.xx)	x.xx (x.xx - x.xx)
Cohort <X>: AX-158<X> mg (N=x)	xxx (xx.xx, xx.xx)	xxx (xx.xx - xx.xx)	x.xx (x.xx - x.xx)

Source Listing: 16.2.5.1; Produced: yyyy-mm-ddThh:mm Page x of y
Treatment: once daily dosing of AX-158 or placebo in a <fasted/fed> state for 10 days, with the final dose administered on the morning of Day 10.
Results obtained using a mixed effects ANOVA on log-transformed data with a fixed effect of study day and a random effect of subject.

AX-158-101

Figure 14.4.2.3

Steady State Least Squares Geometric Mean Ratios and 90% CIs of Plasma AX-158 Concentration Data - Part C (MAD)
PK Set

<Treatment>

Figure Specifications

Plot type: Least squares geometric mean ratios (with 90% CI) overlaid with individual subject ratios.

By: Treatment and comparison - Day 10/Day 5 displayed on one plot, one plot per treatment.

x axis: Parameter

x axis: Label: Comparison

x axis: values: Day 10/Day 5

Y axis: Least squares geometric mean ratio and 90% CI, with individual subject ratios

Y axis Label: Ratio (90% CI)

Y axis values: As appropriate

Legend: N/a

Source Listing: 16.2.5.1; Produced: yyyy-mm-ddThh:mm - Page x of y

Treatment: once daily dosing of AX-158 or placebo in a <fasted/fed> state for 10 days, with the final dose administered on the morning of Day 10.

Results obtained using a mixed effects ANOVA on log-transformed data with a fixed effect of study day and a random effect of subject.

AX-158-101
Table 14.4.2.6
Summary of Statistical Analysis of Plasma AX-158 Accumulation - Part C (MAD)
PK Set

Dose Level	Parameter	n	Geometric LSMeans (95% CI)		Geometric LSMean Ratio (90% C.I.)
			Day 1	Day 10	
Cohort <X>: AX-158 <X> mg (N=x)	C_{\max} (<units>)	x	x.xx (x.xx, x.xx)	x.xx (x.xx, x.xx)	x.xx (x.xx, x.xx)
	$AUC_{0-\tau}$ (<units>)	x	x.xx (x.xx, x.xx)	x.xx (x.xx, x.xx)	x.xx (x.xx, x.xx)
Cohort <X>: AX-158 <X> mg (N=x)	C_{\max} (<units>)	x	x.xx (x.xx, x.xx)	x.xx (x.xx, x.xx)	x.xx (x.xx, x.xx)
	$AUC_{0-\tau}$ (<units>)	x	x.xx (x.xx, x.xx)	x.xx (x.xx, x.xx)	x.xx (x.xx, x.xx)

Source Listing: 16.2.5.7; Produced: yyyy-mm-ddThh:mm - Page x of y

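### Part C steady state rests on a single Day 10/Day 5 trough ratio, mislabelled as consecutive-day comparisons, while other troughs in the SAP's own sampling list stay out of the model

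*SAP*

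**What the plan says.** - **Model.** SAP 11.4.3.3 states that, for each treatment, "log-transformed trough concentration levels at pre-dose on Day 5 and Final Dosing Day (Day 10) will be subjected to" a mixed-effects ANOVA with study day fixed and subject random. The stated aim is to establish whether steady state was attained. Ratios with 90% CIs are given "for the comparisons of each consecutive day (i.e. Day 10/Day 5".
- **Shells.** Table 14.4.2.5 has one ratio column, Day 10/Day 5. The text of 11.4.3.3 asks for the figure "with all treatments on one graph", but the shell for Figure 14.4.2.3 says "Day 10/Day 5 displayed on one plot, one plot per treatment".
- **Sampling.** SAP 11.4.1 lists Part C pre-dose samples on Days 5, 6, 7 and 8 as well as Days 1 and 10. It also lists "Day 2 and Day 11: 24h, 36h", then 48 h (Days 3 and 12) and 72 h (Days 4 and 13). The footnote to the Part C schedule in SAP 3.4.1 says "Pre-dose trough sample day 5 only".
- **BLQ.** For summaries and plots, SAP 11.4.1 says that values below the LLOQ "will be imputed as zero at pre-dose and as LLOQ/2 for post-dose samples". No rule is given for the steady-state model.

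**The concern.** Days 5 and 10 are five days apart, and two days give one contrast. The consecutive-day label therefore does not describe the analysis.

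The single contrast also says little. A ratio above 1 shows that the Day 5 trough was short of plateau, but not whether Day 10 had reached it. A ratio near 1 shows little change after Day 5, but not when the plateau began. The SAP lists samples that could add to this and leaves them out. It also contradicts itself on whether some of them exist.

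The log transform raises a practical problem. Under the summary rule a BLQ pre-dose trough becomes zero, which has no logarithm, while a BLQ 24, 48 or 72 h value becomes LLOQ/2. The same kind of sample would be treated in two ways.

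At stake is how multiple-dose PK, a secondary objective, is described. No error rate is involved.

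**Working it through.** **Which samples exist.** SAP 11.4.1 gives 13 Part C samples on each profile day: pre-dose, 1, 2, 3, 4, 5, 6, 8, 12, 24, 36, 48 and 72 h. With four further pre-dose samples, 2 × 13 + 4 = 30. Protocol v4.0 Table 10.9.6 budgets 29, which equals 14 + 14 + 1 on the protocol's 14-point profile. That fits a Day 5 trough only. Days 6 to 8 are therefore uncertain.

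**Are the 24, 48 and 72 h draws troughs?** For 24 h it is implied, because SAP 11.4.2 derives a Part C Day 1 AUC0-24 as "AUC measured from the concentration at time of dosing to 24 hours post dose". Protocol 10.9.1 gives PK sampling first priority among procedures at a shared time point, but dosing is not named there. The order at 48 and 72 h needs confirming.

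**Precision.** There are 6 active subjects per cohort (SAP 3.3). The within-subject CV is not stated, so 15% and 30% are assumed. The 90% CI multiplier for one ratio is exp(t(0.95, df) × s × √(2/6)), with s = √ln(1 + CV²) and df = 5 × (days − 1). Here s = 0.149 at 15% and 0.294 at 30%.

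| Trough days | df | t | CV 15% | CV 30% |
|---|---|---|---|---|
| 2 (Days 5, 10) | 5 | 2.015 | 1.19 | 1.41 |
| 5 (Days 5–8, 10 or Days 2–5, 10) | 20 | 1.725 | 1.16 | 1.34 |
| 8 (Days 2–8, 10) | 35 | 1.690 | 1.16 | 1.33 |

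From two to five days the log half-width falls by 1 − 1.725/2.015 = 14%, if the variance is the same on every day.

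**Half-life.** None is stated. In a one-compartment model AUC/Cmax ≥ 1/k, so half-life ≤ ln 2 × AUC/Cmax. Taking the exposure limits in protocol 10.8.9 (3.26 µg/mL and 14.859 µg·h/mL) and the starting-dose margins in protocol 8.7:

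- Rat margins: (14.859/69)/(3.26/121) = 0.2153/0.0269 = 8.0 h, so at most 5.5 h.
- Minipig margins: (14.859/41)/(3.26/78) = 0.3624/0.0418 = 8.7 h, so at most 6.0 h.
- Modelled 5 mg AUC of 0.38 (protocol Table 10.8.2) with the minipig Cmax margin: 0.38/0.0418 = 9.1 h, so at most 6.3 h.

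**Expected trough ratios.** With once-daily dosing and linear kinetics, the Day d trough is 1 − r^(d−1) of steady state, where r = 2^(−24/half-life). The 12, 24 and 36 h rows are assumptions.

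| Half-life | Day 10/Day 5 | Day 10/Day 8 | Day 10/Day 2 |
|---|---|---|---|
| 5.5–6.3 h | 1.00 | 1.00 | 1.05–1.08 |
| 12 h | 1.00 | 1.00 | 1.33 |
| 24 h | 1.06 | 1.01 | 2.00 |
| 36 h | 1.17 | 1.02 | 2.66 |

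With five days and CV 15%, an estimate of 1.08 has a lower limit of 1.08/1.16 = 0.93, so Day 2 is not separable from plateau at the projected half-lives. At 12 h the result is mixed: 1.33/1.16 = 1.15, but 1.33/1.34 = 0.99 at CV 30%. At 24 h the rise is clear even at CV 30%: 2.00/1.34 = 1.49.

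**The case against.** The strongest reply is that the SAP promises only whether steady state was attained. At the projected half-lives Day 10/Day 5 is 1.00, so the two-day contrast answers that. This largely stands and is why the point is minor.

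It is also fair that Days 2 to 4 cannot show whether Day 10 is at plateau; they describe early accumulation only. Days 6 to 8 bear on a plateau between Days 5 and 10, but they may not have been drawn. Even if they were, Day 10/Day 8 ratios of 1.00 to 1.02 lie well inside a multiplier of 1.16.

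Other outputs cover part of the ground: concentration summaries by time point, the final-day half-life and the accumulation analysis. The dose-escalation text does not mention this model. None of those outputs, however, gives within-subject ratios between successive trough days with CIs.

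Two stronger readings are tempting. A reader might infer an undeclared departure from the protocol, because v4.0 aims to show when as well as whether steady state is reached. The SAP follows v5.0, which was not among the documents, so this cannot be claimed. A reader might also divide the Cmax limit by the rat margin, pair it with the modelled AUC of 0.38 and obtain a half-life bound of 9.8 h. That mixes sources: 14.859/0.38 = 39 is close to the minipig AUC margin of 41 and not to the rat margin of 69.

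**Conclusion.** The concern holds as a minor one. Three defects need no assumption: the consecutive-day label is wrong, SAP 11.4.1 and the SAP 3.4.1 footnote disagree on Days 6 to 8, and the figure text and shell disagree. The log-scale model also has no workable BLQ rule.

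The analytic gain from adding troughs is modest. The residual df rise from 5 to 20 with five trough days, and the approach to plateau is described by within-subject ratios. The CI figures rest on assumed CVs and a common variance across days. The half-life bounds rest on projected exposures and a one-compartment model.

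A reader might infer that the extra troughs would date the plateau to Day 2 or 3. The protocol's own projections do not support that with 6 subjects. A clear rise from Day 2 would be expected only at longer half-lives, such as the assumed 24 to 36 h.

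**What to change.** 1. Reconcile SAP 11.4.1 with the SAP 3.4.1 footnote on whether pre-dose Days 6 to 8 were drawn.
2. Confirm that the 24, 48 and 72 h draws precede the next dose. Dose times (Listing 16.2.1.2) and actual sample times (Listing 16.2.5.1) allow a check sample by sample.
3. Fit the same mixed model per dose level to all troughs actually drawn: Days 5 and 10, Days 6 to 8 if they exist, and Days 2 to 4 if pre-dose. Pre-specify one set of ratios with 90% CIs, either adjacent sampled days or each day against Day 10.
4. State one BLQ rule for these troughs that can be logged and applies to all of them.
5. Keep the two-day Day 10/Day 5 result as a sensitivity analysis.
6. Correct the consecutive-day wording, update Table 14.4.2.5, and make 11.4.3.3 agree with the Figure 14.4.2.3 shell.

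The cost is SAP wording, one model statement, one BLQ sentence and two shells, with no new samples. The downside is reliance on a common variance structure across days, which the two-day sensitivity result helps to check.
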